4.2.3.2. Exposure and Compliance

Descriptive statistics will be produced to describe the exposure to acalabrutinib specified in section 3.2.2.2 for the safety analysis set:

- Total treatment duration (months)
- Number (%) of patients with total treatment duration
 - ≤ 3 months
 - > 3 months to ≤ 6 months
 - > 6 to ≤ 12 months
 - > 12 to ≤ 24 months
 - > 24 months
- Actual treatment duration (months)
- Actual cumulative dose
- Average daily dose
- Relative dose intensities (%)
- Number of dose withholdings and number (%) of patients with dose withholdings
- Number of dose reductions and number of (%) of patients with dose reductions

4.2.3.3. Adverse events

Treatment-emergent AEs as defined in section 3.2.2.1 will be used for the reporting of the AE summary tables. Any events that occur after a patient has received further therapy for cancer (following discontinuation of study treatment) will be flagged in the data listings. Moreover, AEs occurring more than 30 days after discontinuation of study treatment and any AE occurring before giving the study treatment will be included in the data listings as well.

An overall summary of the number and percentage of patients in each of the aforementioned categories will be presented for the following:

- All TEAEs
- All drug-related TEAEs
- All TEAEs with CTCAE grade ≥ 3
- All drug-related TEAEs with CTCAE grade ≥ 3
- All serious TEAEs

- All drug-related serious TEAEs
- TEAEs leading to treatment discontinuation
- Drug-related TEAEs leading to treatment discontinuation
- TEAEs leading to dose interruption and modification
- TEAEs leading to death
- Drug-related TEAEs leading to death

All AEs will be listed.

A separate listing for adverse events for enrolled but not assigned to treatment patients and for patients who were not exposed to treatment will be created.

4.2.3.3.1. TEAEs and drug-related TEAEs

Treatment-emergent AEs are defined in section 3.2.2.1. TEAEs and drug-related TEAEs will be summarized by system organ class and preferred terms, by CTCAE toxicity grade separately. In addition, TEAEs with CTCAE grade ≥ 3 and drug-related TEAEs with CTCAE grade ≥ 3 will be summarized separately in same manner. Summaries of the TEAEs mentioned above will also be provided by preferred term alone.

4.2.3.3.2. Serious TEAEs and drug-related serious TEAEs

Serious TEAEs and drug-related serious TEAEs will be summarized by system organ class and preferred terms and by CTCAE toxicity grade separately. In addition, summaries of serious TEAEs by preferred term alone will be provided.

4.2.3.3.3. TEAEs and drug-related TEAEs leading to treatment discontinuation

TEAEs and drug-related TEAEs leading to treatment discontinuation will be summarized by system organ class and preferred terms and by CTCAE toxicity grade separately. In addition, summaries of TEAEs and drug-related TAEs leading to discontinuation by preferred term alone will be provided.

4.2.3.3.4. TEAEs leading to dose interruption and modification

TEAEs leading to dose interruption and dose modification (reduced) will be summarized by system organ class and preferred terms and by CTCAE toxicity grade. In addition, summaries of TEAEs leading to dose interruption and modification by preferred term alone will be provided.

4.2.3.3.5. TEAEs leading to death and drug-related TEAEs leading to death

TEAEs leading to death and drug-related TEAEs leading to death will be summarized by system organ class, preferred terms and CTCAE toxicity grade separately. In addition, summaries of TEAEs leading to death and drug-related TEAEs leading to death by preferred term alone will be provided.

4.2.3.3.6. Adverse events of special interest (AESI)

AESIs are defined in sections 3.2.2.1. and 8.1.1.

Summaries of the below-mentioned grouped AE categories will include number (%) of patients who have:

- At least one drug-related AESI
- At least one AESI leading to discontinuation of study medication

AESI, drug-related AESI and AESI leading to discontinuation of study medication will be summarized by grouped term and preferred terms in descending order of frequency and by CTCAE toxicity grade separately.

4.2.3.3.7. Events of Clinical Interest (ECI)

ECIs are defined in sections 3.2.2.1 and 8.1.2.

A summary of the number and percentage of patients with treatment-emergent ECIs will be provided by ECI category and ECI subcategory. In addition, for each ECI category, a separate summary table will be displayed with number and percentage of treatment-emergent ECIs by ECI subcategory and Preferred Term.

4.2.3.3.8. Deaths

All deaths and deaths on-treatment or within 30 days of last dose will be summarized. Details of any deaths will be listed for all patients.

4.2.3.4. Laboratory variables

Project-specific reference ranges will be applied for laboratory variables (hematology, clinical chemistry).

Hematology, clinical chemistry, urinalysis, coagulation, T/B/NK Cell Count, Serum Immunoglobulin will be listed individually by patient and suitably summarized. For all laboratory variables, which are included in the version 5.0 of CTCAE, the CTCAE grade will be calculated.

Numerical laboratory data (absolute and change from baseline) will be summarized by scheduled study day using standard summary statistics (mean, standard deviation, minimum, median, maximum, and number of observations) except for urinalysis.

For hematology and clinical chemistry data shift tables will summarize the change from baseline to maximum on-treatment CTCAE grade, the change from baseline to maximum value, and the change from baseline to minimum value .

Number and percentage of patients with treatment-emergent abnormal hematology and clinical chemistry will be presented by parameter and direction (increased/decreased) for grades ≥ 3 and all grades. To identify potential Hy's Law (see CSP Appendix D for further

details) cases, subjects who have ALT or AST $\geq 3 \times$ ULN together with total bilirubin $\geq 2 \times$ ULN at any time during the study will be flagged in the listings.

Hematological parameters of clinical interest, such as absolute neutrophil count (ANC), hemoglobin, platelets, leukocytes, absolute lymphocyte count (ALC), over time will be plotted for CLL cohort.

A summary of liver function test abnormalities will be provided as follows:

- Number (%) of patients with ALT $\geq 3x$ to $\leq 5x$ ULN, $> 5x$ to $\leq 8x$ ULN, $> 8x$ to $\leq 10x$ ULN, $> 10x$ to $\leq 20x$ ULN and $> 20x$ ULN
- Number (%) of patients with AST $\geq 3x$ to $\leq 5x$ ULN, $> 5x$ to $\leq 8x$ ULN, $> 8x$ to $\leq 10x$ ULN, $> 10x$ to $\leq 20x$ ULN and $> 20x$ ULN
- Number (%) of patients with ALT or AST $\geq 3x$ to $\leq 5x$ ULN, $> 5x$ to $\leq 8x$ ULN, $> 8x$ to $\leq 10x$ ULN, $> 10x$ to $\leq 20x$ ULN and $> 20x$ ULN
- Number (%) of patients with total bilirubin $\geq 2x$ to $\leq 3x$ ULN, $> 3x$ to $\leq 5x$ ULN, $> 5x$ ULN
- Number (%) of patients with potential Hy's Law: (ALT or AST $\geq 3x$ ULN) and Total bilirubin $\geq 2x$ ULN.

Figures of liver biochemistry test results over time for patients with elevated ALT or AST, and elevated total bilirubin will be provided.

Scatter plots for maximum treatment-emergent ALT (xULN) vs. maximum treatment-emergent total bilirubin (xULN) and scatter plots for maximum treatment-emergent AST (xULN) vs. maximum treatment-emergent total bilirubin (xULN) will be presented.

For urinalysis a shift table comparing baseline to the maximum value will be presented.

Analysis of Lymphocytosis (rrCLL cohort only)

For all subjects with baseline and any post-baseline ALC measurements, ALC at peak summary will be provided.

Lymphocytosis is defined as an ALC > 5000 cells per microliter and an increase above baseline. The number of subjects with at least one occurrence of lymphocytosis will be summarized. For subjects with lymphocytosis, resolution of lymphocytosis is defined as 1) a decrease of ALC value to the baseline level or lower, or 2) an achievement of ALC value that is below $5,000/\mu\text{L}$, whichever occurs first. The following analyses will be conducted for subjects with lymphocytosis in RR CLL cohort: ALC at peak and time to peak ALC for subjects who have lymphocytosis will be summarized with descriptive statistics.

Duration of lymphocytosis is defined as the duration of time from the earliest date on which the ALC value met the lymphocytosis criteria at a post-baseline assessment to the earliest date on which a subsequent ALC value met the resolution criteria.

4.2.3.5. Vital signs

Pulse rate, systolic and diastolic blood pressure, body temperature and weight will be listed by patient and summarized using standard summary statistics for the absolute value and change from baseline at each scheduled study visits.

4.2.3.6. ECOG performance status

ECOG performance status specified in section 3.2.2.8 will be summarized by visits.

4.2.3.7. ECGs

Electrocardiogram details will be listed individually by patient. The only ECG data available will be the QTcF, QT and RR results and the overall evaluations, classified as normal, abnormal not clinically significant and abnormal clinically significant. The actual and change from baseline and assessment time (for QTcF, QT and RR measurements) data will be summarized and the overall evaluations will be using shift tables summarising the change from baseline to last on-treatment observation. Graphical presentations of safety data may be presented as is deemed appropriate. This may include, but is not restricted to, presentation of parameters against time, concentration or shift plots. Appropriate scatter plots may also be considered to investigate trends in parameters compared to baseline.

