Subjects should be monitored for signs and symptoms of malignancy. Subjects who develop a second primary malignancy should be managed according to institutional guidelines with diagnostic evaluations as clinically indicated, and it may be necessary for patients to permanently discontinue study treatment. Continuation of acalabrutinib treatment should be discussed with the medical monitor.

Atrial Fibrillation

Events of atrial fibrillation/flutter have occurred in clinical studies with acalabrutinib, particularly in patients with cardiac risk factors, hypertension, diabetes mellitus, acute infections, or a previous history of atrial fibrillation.

Monitor for symptoms of atrial fibrillation and atrial flutter (eg, palpitations, dizziness, syncope, chest pain, dyspnea) and obtain an ECG as clinically indicated. Subjects with atrial fibrillation should be managed per institutional guidelines with supportive care and diagnostic evaluations as clinically indicated.

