8.3.7 Adverse events based on examinations and tests

The results from the Clinical Study Protocol mandated laboratory tests, vital signs, ECGs and other safety assessment will be summarized in the CSR. Deterioration as compared to baseline in these parameters will therefore only be reported as AEs if they fulfil any of the SAE criteria or are the reason for discontinuation of treatment with the investigational product.

If deterioration in a laboratory value, vital sign, ECG or other safety assessment is associated with clinical signs and symptoms, the sign or symptom will be reported as an AE and the associated laboratory result/vital sign will be considered as additional information. Wherever possible the reporting Investigator uses the clinical, rather than the laboratory term (e.g., anemia versus low hemoglobin value). In the absence of clinical signs or symptoms, clinically relevant deteriorations in non-mandated parameters should be reported as AE(s).

Deterioration of a laboratory value, which is unequivocally due to disease progression, should not be reported as an AE/SAE.

Any new or aggravated clinically relevant abnormal medical finding at a physical examination as compared with the baseline assessment will be reported as an AE unless unequivocally related to the disease progression.

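### The ECG shift table uses the last rather than the worst on-treatment evaluation, so a transient, silent abnormality can be missing from it and from the AE tables

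*SAP*

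**What the plan says.** - **ECG outputs (SAP 4.2.3.7).** "The only ECG data available will be the QTcF, QT and RR results and the overall evaluations". The overall evaluation has three levels: normal, abnormal but not clinically significant, and abnormal and clinically significant. It is tabulated in "shift tables summarising the change from baseline to last on-treatment observation". For the intervals, "The actual and change from baseline and assessment time (for QTcF, QT and RR measurements) data will be summarized". In addition, "Electrocardiogram details will be listed individually by patient". Further plots are optional.
- **Laboratory outputs (SAP 4.2.3.4).** Haematology and chemistry shift tables show "the change from baseline to maximum on-treatment CTCAE grade", and also the shifts to the maximum and minimum values.
- **Vital signs (SAP 4.2.3.5).** These are "summarized using standard summary statistics for the absolute value and change from baseline at each scheduled study visits".
- **Extreme values (SAP 4.2.3.1).** A general rule already says that maximum and minimum summaries draw on all on-treatment values, wherever they fall in a visit window, and that unscheduled visits count. No ECG or vital-sign table is specified that uses it.
- **AE reporting (protocol 8.3.7).** "The results from the Clinical Study Protocol mandated laboratory tests, vital signs, ECGs and other safety assessment will be summarized in the CSR". The section infers from this that deterioration in these parameters is an AE only if it meets a seriousness criterion or is why treatment was discontinued. Associated signs and symptoms are still AEs.
- **ECG collection (protocol 8.2.4).** Rhythm, intervals and an overall evaluation are recorded for every ECG. The section tells sites how to report a significant abnormality at screening or baseline, but not one found on treatment.
- **Risk background (protocol 2.3.2.2).** Under important identified risks: "Events of atrial fibrillation/flutter have occurred in clinical studies with acalabrutinib".

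**The concern.** A shift table to the last observation describes where patients ended up, not what happened to them on treatment. A patient whose ECG was abnormal and clinically significant at Cycle 3 and normal at the last on-treatment visit is counted as normal at both ends. The same SAP uses the worst value for laboratory data and gives no reason for treating ECGs differently.

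This matters more here than in most trials because protocol 8.3.7 makes the planned summaries the reason for restricting AE reporting. If the summary discards all but one reading, the reason given for the restriction is weaker than it looks. ECGs are part of the primary safety endpoint in Phase 1 and of the safety endpoint in both Phase 2 cohorts. Atrial fibrillation, which can be intermittent, is one of the drug's important identified risks.

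**Working it through.** The documents state no figure on this point, so the check sets passages side by side, with one count.

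**1. Which ECG summary could reflect a rhythm abnormality?** The SAP says only QTcF, QT, RR and the overall evaluation will be available. With no rhythm variable, the overall evaluation is the only specified ECG summary in which a rhythm disturbance would register as an abnormality. That is the item shifted to the last observation.

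**2. How much of the schedule does that shift use?** On-treatment ECGs in Cohort A through Cycle 12 (protocol Table 2):

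| Visits | Number |
|---|---|
| Cycle 1, Days 8 and 22 | 2 |
| Cycle 2, Days 15 and 28 | 2 |
| Cycles 3 and 4 | 2 |
| Cycles 5 to 12 | 8 |
| Total | 14 |

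The table uses 1 of the 14 for a patient followed to Cycle 12. If exactly one transient abnormal evaluation is assumed, equally likely at any of the 14, the last-observation shift shows it with probability 1/14 = 0.071, about 7%. A worst-on-treatment shift shows it every time, unless the baseline was already in that category. Equal likelihood is an assumption made for illustration.

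**3. Which findings can also escape the AE tables?** Take an on-treatment ECG abnormality and apply the protocol's routes into AE reporting in turn.

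| Feature of the finding | Route into the AE tables |
|---|---|
| Ventricular arrhythmia | AESI whatever its seriousness or causality (protocol 8.3.8); tabulated in SAP 4.2.3.3.6 |
| Meets a seriousness criterion | Reported (protocol 8.3.7) |
| Reason for discontinuing treatment | Reported (protocol 8.3.7) |
| Accompanied by signs or symptoms | The sign or symptom is reported (protocol 8.3.7) |
| Clinically relevant finding at physical examination | Reported (protocol 8.3.7) |
| None of these | No requirement to report |

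The last row is the gap. The tables of events of clinical interest (SAP 4.2.3.3.7) do not close it: they cover cardiac events but are built from AEs, so a finding kept out of AE reporting does not reach them.

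**4. Two mismatches found on the way.**
- Protocol 8.2.3 asks for any clinically significant vital-sign abnormality that is new or worse to be recorded as an AE. Protocol 8.3.7 restricts such reporting to serious or treatment-ending deterioration. Capture of raised blood pressure therefore depends on which section a site follows.
- Protocol 8.2.4 has rhythm recorded for every ECG, while SAP 4.2.3.7 says it will not be available for analysis.

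**The case against.** The strongest reply is that much of the ECG and vital-sign safety signal is captured elsewhere, and this is largely right. A reader might infer that transient arrhythmias and blood-pressure events appear in no summary at all. The documents do not support that, for these reasons:

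- Ventricular arrhythmias are reported and tabulated as AESIs, and symptomatic events are AEs.
- Clinically significant vital-sign abnormalities are AEs under protocol 8.2.3, and hypertension has its own category among the events of clinical interest.
- The standard statistics in SAP 4.1 include minimum and maximum, so an extreme blood pressure or QTcF that enters a visit summary shows in that visit's range. What is missing there is a count of patients. Only the value closest to the scheduled date enters each window.
- ECGs and vital signs are listed by patient, and protocol 9.4.1.1 extends the expert review for other significant AEs to both.
- A site may still choose to record an asymptomatic arrhythmia as an AE, since the general definition in protocol Appendix B is broad. Protocol 8.3.7 simply does not require it.

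What survives is the narrow gap for ECGs. A listing is not a summary, and the expert review selects by judgement. The reply gives no reason for using the last value for ECGs and the worst for laboratory data.

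It is also fair to say that a worst-evaluation shift would not identify atrial fibrillation by name. It would show that a clinically significant ECG occurred. Naming the rhythm needs the variable that the SAP says is unavailable.

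**Conclusion.** The point holds in a limited form. The overall-evaluation shift should use the worst on-treatment category. As planned, an ECG abnormality that follows none of the AE routes and resolves before the last ECG can be absent from the shift table and the AE tables together, leaving the listings and the expert review. The defect is in a descriptive safety table. It does not touch the response-rate analyses or any hypothesis test.

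On size, the firm figure is 1 of 14 scheduled on-treatment ECGs used through Cycle 12 in Cohort A. The 7% chance of display rests on the equal-likelihood assumption. A reader might go further and assume a 1% or 2% abnormality rate per ECG, independent across visits. This gives 1 − 0.99^14 = 13% or 1 − 0.98^14 = 25% of patients with at least one abnormal ECG, against 1% or 2% at the last one. Those rates are not in the documents, and the results describe one table, not events lost to the whole safety report.

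Nor do the documents support 480 ms as an on-treatment QTcF threshold. In protocol 5.2 it is an eligibility limit for QTc averaged over three screening ECGs. Counts by QTcF or blood-pressure category are therefore optional additions.

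**What to change.** **Main change, SAP 4.2.3.7.** Tabulate the overall evaluation as a shift from baseline to the worst on-treatment category, in the order normal, abnormal not clinically significant, abnormal clinically significant. Include unscheduled ECGs and state the on-treatment window. The last-observation shift may be kept beside it.

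**Optional, SAP 4.2.3.5 and 4.2.3.7.** Add numbers and percentages of patients by maximum on-treatment QTcF category and by worst on-treatment blood-pressure category, using the extreme-value rule in SAP 4.2.3.1. Fix and justify the cut-offs in the SAP, since the documents give none for on-treatment values.

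**Reconcile two pairs of passages.** Protocol 8.2.3 with 8.3.7, on when a vital-sign abnormality is an AE. Protocol 8.2.4 with SAP 4.2.3.7, on whether ECG rhythm is available for analysis. If rhythm is available, it should at least be listed and summarised.

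**Cost.** SAP wording and a few tables from data already collected, plus clarification of the protocol passages. The downside is that more abnormal findings will be displayed, including isolated ones that resolved; the retained last-observation shift gives the context for reading them.

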4.2.4. Demographics and Baseline Characteristics

The analysis will be performed separately for all three cohorts: all phase 1 patients, R/R MCL patients (phase 1 and phase 2 combined) and phase 2 R/R CLL patients except where it is mentioned otherwise.

Descriptive summaries of demographics, baseline characteristics, and baseline disease characteristics will be presented for subjects in the safety analysis set. The following will be summarized for all patients:

- Patient disposition (including screening failures and reason for screening failure)
- Important protocol deviations
- Inclusion in analysis sets
- Demographics (age, age group [< 65 , ≥ 65 , < 75 and ≥ 75 years], sex, country, race)
- Patient characteristics (Height, Weight, Body Mass Index)
- Medical and surgical histories
- Other baseline characteristics
 - Simplified MCL international prognostic index (MIPI) (low risk [0-3] vs intermediate risk [4-5] vs high risk [6-11]) – MCL only
 - Ann Arbor staging for lymphoma (1-3 versus 4) - non-CLL only
 - RAI staging – CLL only
 - Patient disease group (MCL, CLL, non-GCB DLBCL, FL, SLL)

- Previous lines of anti-cancer therapies prior to this study (median, 1, 2, ≥ 3)
- ECOG performance status(0, 1, 2, ≥ 3)
- Alcohol use, categorised (never, current, former)
- Nicotine use, categorised (never, current, former)
- Bulky disease (longest diameter of lymph node ≥ 5 cm, ≥ 10 cm at baseline)
- Extranodal disease (yes versus no) – MCL only
- Bone marrow involvement (yes versus no) – MCL only
- Gastrointestinal disease (yes versus no) – MCL only
- $\beta 2$ -microglobulin at baseline (median, ≤ 3.5 mg/L, > 3.5 mg/L) – Phase 2 cohort B only
- IGHV mutation (mutated versus unmutated) – Phase 2 cohort B only
- 17p deletion (yes versus no) – Phase 2 cohort B only
- 11q deletion (yes versus no) – Phase 2 cohort B only
- TP53 mutation (mutated versus unmutated) - Phase 2 cohort B only
- Refractory disease at baseline

The simplified MIPI score will be derived based on baseline values of 4 prognostic factors: age, and ECOG, lactate dehydrogenase (LDH), white blood cell (WBC). Points will be assigned to each of these factors as presented below and the score will be derived by adding the points for all 4 factors. A score of 0-3 indicates low risk, 4-5 indicates intermediate risk, and 6-11 indicates high risk (Hoster 2008).

Points	Age (year)	ECOG	LDH ULN*	WBC, $10^9/L$
0	< 50	0-1	<0.67	<6.7
1	50-59	-	0.67-0.99	6.7-9.9
2	60-69	2-4	1.0 – 1.49	1.0-14.9
3	≥ 70	-	≥ 1.5	≥ 15

*LDH relative to upper limit of normal.

Refractory disease is defined as a lack of at least a partial response to the last therapy before study entry (Wang 2013). Refractory disease will be assessed based on the response to the last MCL treatment regimen a subject received prior to study entry and will be categorized as Yes, No. Subject without achieving at least PR or with unknown response to the last treatment regimen prior to study entry will have a value Yes.

